1.4 Rationale

Based on these vitro and in vivo studies, we propose to evaluate the potential of lenalidomide to overcome rituximab resistance. As pre-clinical data and published clinical data suggest a synergistic effect between lenalidomide and dexamethasone, we propose initial treatment with both drugs for two 28-day treatment cycles (Part I or “priming”) for subjects enrolled to Cohort 1. This combination in itself should have clinical efficacy. The priming phase in Part I will allow the study of immune-modulatory effects on T-cell subsets and cytokine milieu induced by the combination of lenalidomide and dexamethasone prior to the addition of rituximab. A reduced dose of lenalidomide 10 mg daily was chosen as the starting dose, given the heavily pre-treated patient population and the potential for lenalidomide-related myelosuppression. After the first lenalidomide – dexamethasone treatment cycle, the lenalidomide dose can be increased by one dose level based on patient-specific tolerance (see Section 6 for full details). After response assessment following two cycles of lenalidomide – dexamethasone, patients with responsive or stable disease, and patients with progressive disease with an estimated life expectancy of > 3 months will enter Part II with lenalidomide - dexamethasone and rituximab to evaluate the potential reversal of rituximab resistance as measured by response to rituximab and progression-free survival following rituximab.

Subjects enrolled to Cohort 2 of protocol treatment will receive treatment on the same schedule as those subjects in Cohort 1 (10 mg lenalidomide daily, weekly rituximab during Cycle 3), but

weekly dexamethasone will be eliminated from the study treatment plan. Response assessments will be conducted at the same timepoints (at the end of cycles 2 and 5).

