2.2 Secondary Objectives

- 2.2.1 To determine time to progression after lenalidomide + rituximab therapy with and without dexamethasone in relapsed small B-cell lymphomas with rituximab resistance and compare the time to progression for the previous rituximab-containing regimen
- 2.2.2 To compare the response rate for the previous rituximab-containing regimen to that obtained subsequently to lenalidomide + rituximab therapy with and without dexamethasone.
- 2.2.3 To determine the toxicity profile of lenalidomide + rituximab therapy with and without dexamethasone in patients who have received a previous rituximab-containing combination regimen.
- 2.2.4 To correlate Fc γ RIIIa receptor polymorphism profiling with response to lenalidomide - dexamethasone + rituximab therapy in relapsed small B-cell lymphomas with rituximab resistance (Cohort 1 only).
- 2.2.5 To evaluate changes in NK cells, activated NK cells, activated T cells, T regs, and several plasma cytokines following exposure to lenalidomide - dexamethasone and lenalidomide - dexamethasone + rituximab therapy and correlation of observed changes to objective response rates.

[figure not shown]
2.2.6 To determine the presence or absence of minimal residual disease after Part I and Part II of protocol therapy using a PCR-based assay of DNA.

2.2.7 To determine whether 1) a decrease in serum albumin by ≥ 0.3 g/dL at commencement of cycle 2 from baseline predicts a response (CR/PR) to protocol therapy and whether 2) a baseline serum albumin ≤ 4.1 g/dL predicts no response (SD/PD) to protocol therapy.

3 Study Design

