% The lenalidomide dose may be escalated to 15mg daily at the beginning of Cycle 2 of Part I based on patient-specific tolerance as defined in Section 6. The lenalidomide dose during Part II will be determined by dose modification guidelines in Section 6. For patients in Cohort I, the dexamethasone dose during Part II may also be adjusted due to toxicities experienced during Part I. After Part II, patients with SD, PR or CR will continue to receive study treatment as per the schedule above in 28-day cycles until disease progression, development of unacceptable toxicity, or voluntary withdrawal, whichever occurs first.

We plan to include previously treated, histological confirmed follicular lymphoma, marginal zone lymphoma, small lymphocytic lymphoma with <5000 lymphocytes / mm³, lymphoplasmacytic lymphoma with < 3gm/ml IgM or mantle cell lymphoma with confirmation of CD20 antigen expression by flow cytometry or immunohistochemistry on the diagnostic biopsy. Paraffin blocks and/or frozen material from the initial biopsy or biopsy at relapse will be requested in all cases, but are not required for protocol eligibility.

Subjects must have been treated with rituximab in combination with chemotherapy or as monotherapy and must have refractory or progressive lymphoma. Subjects must have had less than a partial response or progressive disease within 6 months of any dose of rituximab.

Subjects must have measurable disease (see Section 3.3). Subjects will need staging to be completed within 60 days prior to registration.

Forty-five subjects will be enrolled to this study. The first twenty-five evaluable subjects will be enrolled to Cohort 1 of study treatment, which will consist of daily dosing of lenalidomide, weekly dosing of dexamethasone and weekly dosing of rituximab during Cycle 3, as described below. Cohort 2 will consist of twenty subjects. These subjects will follow the same treatment schedule as those in Cohort 1, but will not receive weekly dexamethasone.

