Time to progression. We will compute a 95% confidence interval for the ratio of median TTP under revlimid+rituximab to the median TTP under rituximab alone, using the nonparametric method of Jung and Su (1995). If the interval excludes 1, we will declare the difference to be statistically significant.

To evaluate the power of this design, we assumed that TTP in the baseline (rituximab only) period would be statistically independent of TTP in the follow-up (combination treatment) period. This will lead to a conservative estimate of the power, as positive correlation of failure-time endpoints generally increases power for paired comparisons (e.g., see Mick et al. 2000). Assuming that median TTP in the baseline period is 3 months, we calculated the power to detect significance in a test of the null hypothesis that median TTP is the same in both periods. If the median TTP in the follow-up period is doubled, to 6 months, then the power is 83%; if the median TTP is tripled, to 12 months, then the power is essentially 100%. Thus power is satisfactory if there is a substantial increase in the median TTP.

Design and analysis of correlative studies. In correlative studies, we will compare mean changes in immunologic phenotype parameters (fraction Th2⁺ cells, NK cells and Treg cells) between the subjects who experience a remission (expected to be up to 80%, or 36 of 45 subjects) and those who do not (as few as 20%, or 9 of 45 subjects). As we do not yet know the likely values of these immunologic parameters, we estimate the power in terms of the difference in means as a fraction of the common standard deviation (SD). The basic analysis is a t test comparing mean change in the two groups. Calculations show that if the standardized difference is equal to 1 SD, then the power is 75%, whereas if the standard difference is 1.25 SDs, then the power is 91%. Thus the power of this correlative analysis is reasonable as long as there is a reasonably large difference in mean change between the remission and non-remission groups.

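### The immune correlative t test pools subjects treated with and without weekly dexamethasone and ignores cohort, a potential confounder; adding a cohort term is a cheap improvement

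*Combined protocol and SAP*

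**What the plan says.** Section 8 (Design and analysis of correlative studies) compares mean changes in immune-cell fractions by remission status. One group consists of those "who experience a remission (expected to be up to 80%, or 36 of 45 subjects"; the remaining 9, or 20%, form the comparison group. The method is stated in one sentence: "The basic analysis is a t test comparing mean change in the two groups". Power is given as 75% for a standardized difference of 1 SD and 91% for 1.25 SD. No cohort term, stratum or cohort-specific analysis is named.

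Sections 3.1 and 8 make up the 45 from 25 subjects in Cohort 1 and 20 in Cohort 2. The first 25 evaluable subjects go to Cohort 1, so allocation is sequential and not randomized. Of Cohort 2, Section 3.1 says: "These subjects will follow the same treatment schedule as those in Cohort 1, but will not receive weekly dexamethasone".

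Both cohorts supply data. Section 3.1 has samples for the ancillary studies taken from all subjects, and in the Section 3.3 table the blood and plasma row lacks the Cohort-1-only mark that the FcR row carries. Section 1.4 describes the correlative aim as covering treatment with and without dexamethasone. Objective 2.2.5, however, names only changes "following exposure to lenalidomide - dexamethasone and lenalidomide - dexamethasone + rituximab therapy" and, unlike 2.2.4, is not restricted to Cohort 1.

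**The concern.** For cohort to distort the comparison it must be related both to the immune change and to remission. The protocol's own reasoning makes each link plausible. Section 1.4 says that Part I allows study of "immune-modulatory effects on T-cell subsets and cytokine milieu induced by the combination of lenalidomide and dexamethasone", and Cohort 2 does not receive that combination. Sections 1.2 and 1.4 argue that dexamethasone acts synergistically with lenalidomide against the tumor, so remission could be more frequent in Cohort 1.

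If both links exist, the remission and non-remission groups contain different shares of dexamethasone-treated subjects. The pooled difference then mixes a regimen effect with the association of interest. It can create an apparent immune correlate of response or cancel a real one, depending on the sign of the shift. If only the first link exists there is no bias, but the difference between cohorts inflates the SD used by the test and power is lost. At stake is the reading of the analysis that asks whether immune change tracks response.

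**Working it through.** **Inputs.** From the documents: 25 and 20 subjects; 36 remissions and 9 non-remissions; differences of 1 and 1.25 SD; stated power 75% and 91%. The significance level for this test is not stated, so two-sided 5% is assumed; Section 8 gives that level only for the albumin analysis. Also assumed, because the documents give no value: dexamethasone shifts the mean immune change by δ within-cohort SDs, with δ = 0.5 or 1 in either direction. The split of the 36 remissions between cohorts is varied.

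**1. The plan's own figures.** For a two-sample t test with 43 df, noncentrality = d × √(36 × 9 / 45) = d × √7.2 = 2.683d.
- d = 1: power 74.6%.
- d = 1.25: power 90.6%.

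Both match the stated 75% and 91%. A one-sided test would give 84.0% and 95.1%, so two-sided 5% is the fitting reading.

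**2. Bias of the pooled difference.** Bias = δ × (share on dexamethasone among remitters − share among non-remitters).

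| Remissions, Cohort 1 / Cohort 2 | Remitters on dex. | Non-remitters on dex. | Bias at δ = 1 |
|---|---|---|---|
| 20/25, 16/20 | 20/36 = 0.556 | 5/9 = 0.556 | 0 |
| 22/25, 14/20 | 22/36 = 0.611 | 3/9 = 0.333 | 0.28 SD |
| 23/25, 13/20 | 23/36 = 0.639 | 2/9 = 0.222 | 0.42 SD |
| 24/25, 12/20 | 24/36 = 0.667 | 1/9 = 0.111 | 0.56 SD |

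**3. Effect on the pooled t test.** Simulation, 40,000 runs per scenario, within-cohort SD of 1, two-sided 5%. The false-positive rate assumes no true association; power assumes a true 1-SD difference.

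| Remissions | False positives, δ = 0.5 | False positives, δ = 1 | Power, δ = −1 |
|---|---|---|---|
| 20/25, 16/20 | 4.5% | 2.8% | 66.7% |
| 22/25, 14/20 | 5.8% | 7.7% | 38.4% |
| 23/25, 13/20 | 7.8% | 14.5% | 26.0% |
| 24/25, 12/20 | 10.3% | 24.2% | 16.5% |

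With equal remission rates and δ = +1, power is 66.3% (72.6% at δ = 0.5). The reason is the inflated SD: cohort adds about δ² × (25/45) × (20/45) = 0.247 to the variance, so the SD that the test uses is about √1.247 = 1.12.

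Masking needs the shift and the remission difference to point in opposite directions. It arises with more remissions in Cohort 1 and a negative shift, as in the table. It arises equally with more remissions in Cohort 2 and a positive shift: at 18/25 against 18/20, power is 38.6% for δ = 1 and 59.8% for δ = 0.5.

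**4. The cohort-adjusted model.** In a linear model of change on remission plus cohort (42 df), the noncentrality at d = 1 is √W. W sums, over cohorts, remitters × non-remitters / cohort size.
- 20/25, 16/20: W = 20×5/25 + 16×4/20 = 7.20; power about 75%.
- 22/25, 14/20: W = 22×3/25 + 14×6/20 = 6.84; power about 72%.
- 23/25, 13/20: W = 23×2/25 + 13×7/20 = 6.39; power about 70%.
- 24/25, 12/20: W = 24×1/25 + 12×8/20 = 5.76; power about 65%.

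In the simulation its false-positive rate stayed at about 5% in every scenario, whatever the shift.

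**5. Separate tests by cohort.** At 80% remission, power for 1 SD is 48% in Cohort 1 (20 against 5) and 40% in Cohort 2 (16 against 4). Adjustment is more workable than splitting.

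**The case against.** The strongest objection is that nothing in the documents shows that dexamethasone itself changes NK, Th2 or Treg cells. The dexamethasone data in Section 1.2 are anti-proliferative effects in lymphoma cell lines. The immune data in Sections 1.1.5 and 1.2 concern lenalidomide or its drug class, and Section 1.4 does not separate the components of the combination. This stands. A reader might infer that cohort is an established confounder, but the documents support only a potential one, and every distorted figure above depends on an assumed shift.

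Second, a reader might infer that the stated 75% is wrong. It is not. The plan expresses the difference in units of a common SD because it does not know the immune values, and on that basis both power figures reproduce. The 66% applies only if the SD is read as within-cohort and a 1-SD shift exists.

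Third, objective 2.2.5 asks for a correlation. If dexamethasone raised remission through immune change, part of the pooled association would be a genuine correlate of response, and a cohort term would remove it. This stands, and is a reason to keep the unadjusted comparison beside the adjusted one.

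Fourth, Section 8 calls the t test the basic analysis, and Section 3.5 lets the principal investigator alter the correlative studies. Both leave room for a cohort analysis, but neither specifies one. The analysis is secondary, and no decision rule is attached to it.

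**Conclusion.** The point holds as a conditional one. The plan specifies an unadjusted comparison across two sequentially enrolled regimens when a recorded variable, cohort, may be related to both sides of it. Creating or masking an association requires a dexamethasone effect on the immune measure and different remission rates by cohort; loss of power through added variance requires only the first.

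With a 1-SD shift and 36 remissions, the consequences range from a power loss of about 9 points without bias (equal rates) to a false-positive rate of about 24%, or power of about 16%, at the most unequal split examined. At 0.5 SD the false-positive rate is 6% to 10% over the same unequal splits, which is modest. The documents give neither the shift nor the cohort remission rates, so these figures are ranges and not forecasts. Nor do the calculations support an inference that adjustment always restores 75% power; that holds only when the cohort remission rates are equal. This is an inexpensive improvement to a secondary analysis, and the primary response conclusion is unaffected.

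**What to change.** In Section 8, make the main correlative analysis a linear model of change on remission status plus cohort, and use the same cohort term for the plasma cytokine analyses. Report mean changes within each cohort. Keep the unadjusted t test as supportive, and say that a gap between the two results may reflect either confounding by regimen or a genuine correlate of response that runs through dexamethasone.

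Reconcile objective 2.2.5, which names only the regimen with dexamethasone, with Section 1.4 and with the 45-subject analysis in Section 8, both of which cover the two cohorts.

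The cost is a few sentences and no new data. Statistically it is one degree of freedom plus the collinearity between cohort and remission: power at 1 SD stays at about 75% with equal remission rates and drops to about 65% to 72% when they differ at 36:9. The power paragraph should state this and say that its 75% and 91% assume no cohort effect.

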7.12 Safety evaluation

Data from all subjects who receive any study drug will be included in the safety analyses. Subjects who entered the study and did not take any of the study drug(s) and had this confirmed, will not be evaluated for safety.

The severity of the toxicities will be graded according to the NCI CTCAE v3.0 whenever possible.

8 Statistical Plan

Statistical design and analysis

Design. This study will enroll 45 evaluable subjects, all of whom have had lymphoma progression or failure to respond within six months of being treated with rituximab alone or with a rituximab-containing regimen. Twenty-five patients will be enrolled into Cohort 1, which will consist of daily dosing of lenalidomide and weekly dosing of dexamethasone. An additional twenty patients will be enrolled into Cohort 2, in which patients will receive daily dosing of lenalidomide, but will not be treated with weekly dexamethasone. Subjects with documented Rituxan-refractory disease will be enrolled to the study and treated for two 28-day cycles with lenalidomide – dexamethasone (Cohort 1) or lenalidomide alone (Cohort 2). After this first treatment period, termed Part I, subjects will be re-evaluated and subsequently treated with

lenalidomide – dexamethasone and rituximab (Cohort 1) or lenalidomide and rituximab (Cohort 2) in combination. A subject who does not complete rituximab therapy as part of this study will be considered non-evaluable and may be replaced by enrolling an additional subject. However, all subjects will be included in the intent-to-treat analysis.

Power to detect adverse effects. With 45 subjects, we will have 90% power to detect any unforeseen toxicity whose prevalence is at least 5.0%. The half-width of the confidence interval for any fraction (toxicity or response) will extend no more than +/- 15% around the estimate.

Treatment response. We will use McNemar's test to compare the fractions of patients responding to rituximab therapy without (baseline) and with revlimid. In the baseline period, we estimate that 10% of patients will have responded to rituximab, although all will ultimately fail within 6 months. Assuming a modest kappa (intra-subject correlation) of 10%, with 45 patients we have 87% power to detect a significant effect of revlimid treatment if the treatment-period response rate is 35%.

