Analysis of serum albumin as a biomarker. We will test the hypotheses that 1) a decrease in serum albumin by ≥ 0.3 g/dL at commencement of cycle 2 from baseline predicts a response (CR/PR) to protocol therapy and that 2) a baseline serum albumin ≤ 4.1 g/dL predicts no response (SD/PD) to protocol therapy. From preliminary analysis of our first eleven patients, we will assume the same breakdown of responses (3 non-responders: 8 responders). Using this

assumption, we will have 80% power with a two-tailed alpha of 0.05 to detect an odds ratio of 2.6; this is 10 times less than expected.

9 Safety and Adverse Events

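### The albumin biomarker analysis claims 80% power for an odds ratio of 2.6, but for its two yes/no markers 45 patients give at most about 26% (Fisher) or 30% (chi-square)

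*Combined protocol and SAP*

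**What the plan says.** Objective 2.2.7 and the paragraph on serum albumin in Section 8 set out two hypotheses. The first is that an albumin fall of at least "0.3 g/dL at commencement of cycle 2 from baseline predicts a response (CR/PR) to protocol therapy". The second is that a baseline albumin at or below 4.1 g/dL "predicts no response (SD/PD) to protocol therapy".

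For power, Section 8 says "From preliminary analysis of our first eleven patients, we will assume the same breakdown of responses (3 non-responders: 8 responders". On that basis "we will have 80% power with a two-tailed alpha of 0.05 to detect an odds ratio of 2.6", and of this odds ratio it adds: "this is 10 times less than expected".

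The paragraph gives no sample size of its own, names no test, gives no prevalence for either marker, and does not say what unit the odds ratio refers to. The trial total is in the design paragraph of Section 8: "This study will enroll 45 evaluable subjects".

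**The concern.** Each hypothesis, as written, is a 2×2 table: marker present or absent against response or no response. With 45 patients, about 12 of them non-responders, such a table carries little information, and an odds ratio of 2.6 is a moderate effect. A power of 80% looked far too high.

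Two statements depend on it: the detectable effect and the tenfold safety margin. If both are wrong, a null result would be read as excluding moderate associations when the analysis had little chance of finding them. The reassurance given by the margin would also depend on a marker prevalence that the plan never states.

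**Working it through.** **Inputs.** From the albumin paragraph: odds ratio (OR) 2.6, two-sided alpha 0.05, response rate p = 8/11, and an expected OR of about 10 × 2.6 = 26, reading the margin as a ratio. From the design paragraph: N = 45, which is an assumption for this analysis. The split is 45 × 8/11 = 32.7 and 45 × 3/11 = 12.3, so 33 and 12. Marker prevalence m is not given and is varied.

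**Step 1. Reproducing the plan's figure.** The usual logistic-regression formula for a continuous predictor, with the OR per standard deviation (SD), is

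power = Φ(√(N·p·(1−p))·ln OR − 1.96).

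With p(1−p) = 0.1983 and ln 2.6 = 0.9555: √(45 × 0.1983) × 0.9555 = 2.855, and Φ(2.855 − 1.96) = 81.5%. The required N is (1.96 + 0.842)² / (0.1983 × 0.9555²) = 43.3, and the OR detectable with 80% power at N = 45 is 2.55. This agrees with the plan's 80% and 2.6. The formula is an approximation: simulating that logistic model at N = 45 gave 69% (Wald test) and 75% (likelihood-ratio test).

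**Step 2. The yes/no markers.** Let q1 = P(marker | response) and q0 = P(marker | no response). For each m, solve

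(8/11)·q1 + (3/11)·q0 = m and [q1/(1−q1)] / [q0/(1−q0)] = OR.

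For example, m = 50% and OR 2.6 give q1 = 0.563 and q0 = 0.332. Power is the sum of Binomial(33, q1) × Binomial(12, q0) probabilities over all tables with two-sided p ≤ 0.05.

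| Overall prevalence (marker of response) | Power for OR 2.6, Fisher / chi-square | Smallest OR with 80% power, Fisher / chi-square (rounded up to a tenth) | Fisher power for OR 26 |
|---|---|---|---|
| 20% | 6.6% / 11.0% | not reached (42% / 57% even at OR 1000) | 34% |
| 30% | 15.3% / 19.5% | 29.7 / 18.7 | 78% |
| 40% | 22.0% / 23.7% | 11.0 / 10.2 | 94% |
| 50% | 25.5% / 27.5% | 8.2 / 7.8 | 98% |
| 60% | 24.6% / 29.7% | 7.8 / 7.0 | 99% |
| 70% | 22.1% / 28.2% | 8.4 / 7.3 | 99% |

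The maximum over all prevalences is 25.6% (Fisher) and 29.7% (chi-square). For a marker of non-response, read the table at 1 minus the prevalence, because absence of that marker is a marker of response with the same OR.

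**Step 3. Other choices.** Maximum power for OR 2.6, Fisher / chi-square:

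- Rounding the split to 32 and 13: 28.0% / 30.2%.
- 36 and 9, the remission rate in the correlative-studies paragraph ("expected to be up to 80%, or 36 of 45 subjects"): 22% / 29%.
- 16 and 29, from the 35% treatment-period response rate in Section 8: 26% / 34%.
- An almost equal split, 22 and 23: 30% / 35%.

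At 33 and 12, a likelihood-ratio test reaches 31.8%, and a one-sided normal approximation 40.6%.

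**Step 4. Sample size needed.** By the normal approximation for two proportions at 8:3, 80% power for OR 2.6 needs about 176 patients at 60% prevalence, 179 at 50% and 245 at 30%.

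**Step 5. The margin.** At the most favourable prevalence, 26 / 7.8 = 3.3 (Fisher) and 26 / 7.0 = 3.7 (chi-square), against the claimed 10.

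**The case against.** The best reply is that the figure is not a miscalculation. It follows from a standard formula for a continuous predictor, so the fault may be only an unlabelled unit and an unnamed test. The contradiction also needs inputs that the plan does not supply: a sample size, a 2×2 test and a prevalence. Because replaced subjects stay in the intent-to-treat analysis, more than 45 could be analysed. The expected odds ratio of 26 is inferred and not stated. Finally, if the effect really is that large, power is good over most prevalences.

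Much of this stands. The 80% is probably correct arithmetic for another analysis, though the plan does not say so. N = 45 and the expected odds ratio of 26 are assumptions, and the practical weight is limited.

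It does not rescue the statement. The hypotheses are written as cut-points, and an odds ratio per SD is not the odds ratio of a cut-point marker. The power figures are maxima over the unknown prevalence. A few replacement patients would not close a gap between 45 and about 176. At the expected effect, power is still only 34% (Fisher) if a marker of response is present in 20% of patients.

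**Conclusion.** The concern holds: the power statement is wrong for the analysis described. With 45 patients and a split of 33 to 12, power for an odds ratio of 2.6 is at most 25.6% (Fisher) or 29.7% (chi-square). None of the other splits or two-sided tests tried exceeds about 35%. The smallest odds ratio with 80% power is about 7 to 8 at 50–60% prevalence and rises steeply for less common markers of response. The tenfold margin is about three- to fourfold at best.

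This rests on N = 45, on testing the markers as yes/no variables, and on reading the expected odds ratio as 26. The statement should be corrected, but nothing in the trial's size, primary endpoint or treatment depends on it.

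**What to change.** State the sample size, the test, the assumed prevalence of each marker and the unit of the odds ratio. Replace 2.6 with the detectable odds ratio for the yes/no markers, preferably as a short table. For a marker of response: about 7–8 at 50–60% prevalence, 10–11 at 40% and 19–30 at 30%, mirrored for a marker of non-response. Restate the margin with its assumptions, including the expected odds ratio; on the reading used here it is three- to fourfold at best.

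An alternative is to make logistic regression on continuous albumin the main albumin test and label 2.6 as per SD. That changes the question asked in objective 2.2.7 and should be a deliberate choice.

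A secondary query: did the 0.3 and 4.1 g/dL cut-offs, or the expected odds ratio, come from the first eleven patients? The text takes only the response split explicitly from them. If they did, also report the test in the 45 − 11 = 34 later patients, beside the full analysis and not in place of it. At an odds ratio of 26, its Fisher power for a marker of response (split left random) is about 87% at 50% prevalence, 47% at 30% and 14% at 20%.

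The cost is a text correction and a less favourable power figure. No extra patients or procedures are needed.
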